The long-term goal of the ENLACE is to reduce obesity and obesity-related morbidity and mortality by increasing the number of Latinas who meet national PA guidelines for adults9. We hypothesize that Latinas at the PA intervention sites will significantly increase their MVPA levels as a result of addressing their specific individual and environmental barriers and enhancing their social support and collective efficacy, compared to Latinas at the attention-control sites.

Primary aim: Test the effect of a 16-week, promotora-led PA intervention on minutes per week of MVPA (primary outcome) among Latinas in South Texas, compared to an attention-control group.

Secondary aims: a) Test the effect of the 16-week promotora-led PA intervention on physical fitness and weight maintenance (secondary outcomes); b) assess the maintenance of primary and secondary outcomes 6 months after the end of the intervention; c) examine the role of self-efficacy for PA, social support, decisional balance, and collective efficacy as mediators of changes in MVPA; and d) evaluate the impact of Latinas' social and community environment context on their success (or failure) in increasing MVPA and maintaining the behavior change.

Eight community resource centers (CRCs) in four Lower Rio Grande Valley (LRGV) counties—Starr, Hidalgo, Willacy and Cameron—will be randomly assigned to either the ENLACE PA Intervention (4 CRCs) or the attention-control condition (4 CRCs). We will recruit 864 Latinas ages 18 - 64 who do not meet national PA guidelines from colonias (unincorporated settlements where many people live in impoverished conditions and lack basic services) in the service area of the eight CRCs. Participants from CRCs randomized to the ENLACE PA Intervention (N = 432; 108 women per CRC) will receive the 16-weekly promotora-led group sessions, followed by 24 weeks of a maintenance intervention (monthly promotora-delivered newsletter and bi-monthly telephone counseling). The goal for the 16 weeks will be for women to engage in 30 minutes per day of MVPA on 5 or more days per week. The attention-control group (N = 432; 108 women per CRC) will receive 8 promotora-led group sessions twice a month on home safety/first aid and monthly generic health education materials during the maintenance intervention period. Standardized measurement of primary and secondary outcomes will occur at baseline, immediate (16 weeks) and delayed (40 weeks) post-intervention.

2. Background.

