D.2.4.2. ENLACE PA Intervention Activities. Consistent with national PA guidelines, participants randomized to the *ENLACE* PA intervention will be encouraged to engage in moderate to vigorous intensity PA for 30 minutes on 5 or more days per week. The *promotora*-led intervention will consist of 16 weekly sessions that include 30 minutes of group health education plus 30-45 minutes of group exercise. The sessions address the determinants of knowledge, perceived barriers and benefits, behavioral skills, self-efficacy, reinforcement and social support for the behavioral outcome of increasing MVPA. Didactic approaches include information provision, discussion, active learning, guided practice, self-reevaluation, and modeling. Participants will receive a pedometer and a set of resistance bands (3 resistance levels). *Promotoras* will demonstrate the use of pedometers, walking techniques, strength exercises with resistance bands, and self-assessment of exercise exertion level. Participants will start their PA program slowly, gradually increasing both frequency and intensity over the 16 weeks in order to meet the study goal. Pedometers will be used as a PA self-monitoring and motivational enhancement tool. The *promotora* will advocate using steps per day as part of goal setting activities (e.g., focusing on increasing steps per day through bouts of walking). Women in the *ENLACE* pilot preferred (1) incorporating group exercise as a part of the health education sessions and (2) brisk walking and Zumba[®]. *Promotoras* will be trained to lead group exercise activities and will have access to an exercise DVD library, resistance bands, and yoga mats. These PA options and resources will also be available at the CRCs for participants’ use outside the scheduled intervention sessions. In addition, *promotoras* will use the Volunteer Walk Leader Manual to recruit and train a cadre of volunteers to lead walking groups at the CRC. This manual, developed at the University of South Carolina, was translated into Spanish for use in the pilot study. (A copy of the manual is in Appendix C.)

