Mediation Analyses (Aim 2c). As outlined by MacKinnon^{103, 104}, mediation will be assessed by conducting two regression models. The first model will regress change in the hypothesized mediator (e.g., social support, self-efficacy) on intervention group (intervention vs. control) (α coefficient path). The second model will regress change in the outcome variable (e.g., MVPA) on intervention group and change in the hypothesized mediator (β coefficient path). To assess the magnitude of the effect for each potential mediator, the Sobel-Goodman test will be conducted using *sgmediation* in STATA 11 SE¹⁰⁵. This method provides direct and indirect effect estimates, proportion of effect explained by mediator, and significance testing.

Attrition Analyses. We will compare all baseline demographic, cognitive, and behavioral variables of participants lost to follow-up with baseline data of the cohort, to determine possible selective or differential (by treatment condition) attrition. For instance, analyses will be conducted to determine if participants with greater weight or lower PA disproportionately drop out of the study. Selective attrition (i.e., do dropouts differ from the cohort as a whole?) will be considered a threat to external validity or generalization. Presence of differential attrition (i.e., difference in dropouts between treatment conditions) will be considered a threat to internal validity. To the extent that some subjects are lost to follow-up, analysis for the primary and secondary hypotheses will be carried out under the intent-to-treat principle.

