Hispanics/Latinos experience a disproportionate burden of obesity-related chronic diseases, threatening the future health of the nation's fastest-growing population. Physical inactivity has been linked to increased risk of obesity, type 2 diabetes, and various cancers. Latinos are more likely than non-Hispanic whites to fail to meet physical activity (PA) recommendations, and Latino women are less physically active than Latino men. The **goal** of the proposed *ENLACE* research project is to design, implement and evaluate a *promotora*-led PA intervention that takes a comprehensive, multi-level, community-based approach to promoting moderate-to-vigorous physical activity (MVPA) among a particularly underserved segment of Latinas. The intervention approach, based on the social ecological model, focuses on individual attitudes and skills, socio-cultural factors and environmental influences to behavior change. The proposed group-randomized controlled trial builds on formative and pilot research (funded by a National Heart, Lung and Blood Institute R21, HL087765) by a team of academic investigators and community partners with extensive experience working together to conduct behavioral interventions and outreach with Latino and disadvantaged populations. Eight community resource centers (CRCs) in four predominantly Latino counties in South Texas' Lower Rio Grande Valley will be randomly assigned to either the *ENLACE* PA Intervention (4 CRCs) or an attention-control condition (4 CRCs). We will recruit 864 Latinas ages 18-64 who do not meet national PA guidelines from *colonias* (unincorporated, impoverished, underserved Latino settlements) in the CRC service areas. Participants from CRCs randomized to the *ENLACE* PA Intervention (N = 432; 108 women per CRC) will receive 16 weekly *promotora*-led group sessions followed by 24 weeks of a maintenance intervention (monthly *promotora*-delivered newsletters and telephone counseling twice a month). The group sessions' behavioral goal is for Latinas to engage in 30 minutes per day of MVPA on 5 or more days per week. The attention-control group (N = 432; 108 women per CRC) will receive 8 *promotora*-led group sessions twice a month on home safety/first aid and monthly generic health education materials during the maintenance intervention period. The primary outcome is minutes per day of MVPA (measured with accelerometers). Secondary outcomes are physical fitness and weight maintenance. We also will evaluate self-efficacy, social support, decisional balance, collective efficacy and food frequency as mediators of MVPA changes. Standardized measurement of primary and secondary outcomes will occur at baseline, immediate (16 weeks) and delayed post-intervention (40 weeks). We **hypothesize** that Latinas in the *ENLACE* PA Intervention will significantly increase their MVPA levels as a result of addressing their specific individual, socio-cultural and environmental barriers and enhancing their social support and collective efficacy, compared to attention-control Latinas.

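### Aim 2c tests each mediator in a model of its own, which cannot separate correlated mediators and can give overlapping proportions explained; a joint multiple-mediator model should be added

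*Protocol*

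**What the plan says.** Section 1 of the protocol (Secondary aims, item c) sets out to "examine the role of self-efficacy for PA, social support, decisional balance, and collective efficacy as mediators of changes in MVPA". That is four constructs. The Abstract / Project Summary lists five: "We also will evaluate self-efficacy, social support, decisional balance, collective efficacy and food frequency as mediators of MVPA changes".

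Section 6.a, Mediation Analyses (Aim 2c), fixes the method: "mediation will be assessed by conducting two regression models". The first regresses change in a mediator on arm. For the other, "The second model will regress change in the outcome variable (e.g., MVPA) on intervention group and change in the hypothesized mediator", with the mediator in the singular. Then, "To assess the magnitude of the effect for each potential mediator", it runs a Sobel-Goodman test, using the Stata command sgmediation. On the output it adds: "This method provides direct and indirect effect estimates, proportion of effect explained by mediator, and significance testing".

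The section describes no model that holds several mediators at once and no adjustment of one mediator for the others. It does not say that the proportions will be summed or read as shares of a whole.

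On what the programme is meant to move, D.2.4.2 (ENLACE PA Intervention Activities) says: "The sessions address the determinants of knowledge, perceived barriers and benefits, behavioral skills, self-efficacy, reinforcement and social support". The hypothesis in section 1 adds collective efficacy, next to social support, as a route to higher MVPA.

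**The concern.** One programme is designed to shift several psychosocial constructs together. They are reported by the same women at the same assessments, and most of them concern physical activity. If two of them rise together and only one drives MVPA, a model holding arm and the other one alone will still show a mediator slope, because that mediator stands in for the one left out. Its indirect effect, Sobel test and proportion explained then carry an effect that is not its own.

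This is omitted-variable bias in the estimate. A larger sample does not remove it, and neither does a correction for multiple testing. At stake is whether Aim 2c can tell a mechanism that works from one that merely moves with it.

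**Working it through.** **Inputs from the protocol.** The mediation section states no numerical target, so there is no figure of the plan's own to reproduce. Power and Sample Size gives 83 evaluable women per site; with 8 sites, 8 × 83 = 664. Aim 2c names four mediators.

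**Assumed inputs (not in the documents).**
- Four mediators with unit residual variance and a common correlation r after adjustment for arm. Values of 0, 0.2, 0.3 and 0.5 are shown.
- One active mediator, moved a = 0.3 SD by the programme, with slope b = 0.3 on MVPA.
- Three inert mediators with slope 0, moved 0.3 SD or less.
- Direct effect of arm 0.2; two-sided test at 1.96; no clustering; mediators measured without error.

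**Step 1: slope in a one-mediator model.** With the others left out, the slope for mediator k is b_k + Σ r·b_j, summed over the other mediators. For an inert mediator this is r × 0.3, or 0.06, 0.09 and 0.15 at r = 0.2, 0.3 and 0.5. The true value is 0.

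**Step 2: proportions explained.** The total effect is 0.3 × 0.3 + 0.2 = 0.29, so the true mediated share is 0.09 / 0.29 = 31%. Each inert mediator moved 0.3 SD is credited with 0.09·r / 0.29, and the four proportions total 0.09 × (1 + 3r) / 0.29.

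| r | share credited to each inert mediator | total of four proportions | true mediated share |
|---|---|---|---|
| 0 | 0% | 31% | 31% |
| 0.2 | 6% | 50% | 31% |
| 0.3 | 9% | 59% | 31% |
| 0.5 | 16% | 78% | 31% |

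**Step 3: how often an inert mediator passes the Sobel test.** The statistic is a·b / √(a²·SE_b² + b²·SE_a²). Simulated trials of 664 women gave these rates per inert mediator, accurate to within a few percentage points:

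| programme effect on the inert mediators | r = 0.2 | r = 0.3 | r = 0.5 |
|---|---|---|---|
| 0.3 SD | 19% | 42% | 87% |
| 0.2 SD | 9% | 22% | 54% |
| 0.1 SD | 2% | 5% | 15% |
| none | 0.3% | 0.6% | 3% |

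With all four mediators in one model, the rate is about 2% or less in every cell. At r = 0 the separate models also give about 2% with a 0.3 SD movement. With that movement, at least one of the three inert mediators passes in 44%, 76% and 98% of trials at r = 0.2, 0.3 and 0.5.

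**Step 4: sensitivity to the other assumptions.**
- Adding an intraclass correlation of 0.01 changes the 0.3 SD row little (18%, 41%, 80%).
- If r is a correlation between error-free scores and the mediators have reliability 0.7, the 0.3 SD row falls to 10%, 23% and 60%. At reliability 0.5 it falls to 5%, 12% and 36%. The protocol's test-retest figures are 0.43 to 0.68 for self-efficacy and 0.55 to 0.86 for social support.
- A stronger active mediator (b = 0.4) with no direct effect gives 33%, 68% and 94%. The four proportions then total 1 + 3r, that is 160%, 190% and 250%.

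**The case against.** **The harm is not certain.** A reader might infer that the plan does count the same effect several times and does make inert mediators look active. The documents do not support that. They give no correlation between mediators and no size for the programme's effect on any of them. Without residual correlation the separate models work, and a mediator that the programme does not move rarely passes the test. This objection stands: the rates are conditional, and those near 87% lie at the unfavourable end of the range.

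**Totals above 100%.** A reader might also infer that the proportions will exceed the whole effect. That depends on the direct effect: the totals are 50% to 78% with a direct effect of 0.2, and pass 100% in the case with none. The protocol never adds the proportions, so double counting arises only if they are read as additive shares. Each proportion can still be inflated on its own.

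**The two models answer different questions.** Aim 2c asks about the constructs' role as mediators and does not ask for effects independent of one another. If one construct acts through a second, the joint model can miss it. With an assumed path of 0.5 from the first to the second and 0.4 from the second to MVPA, the first has slope 0.5 × 0.4 = 0.20 alone and 0.00 jointly. This also stands. It is a reason to show both sets of results, and it does not rescue single-mediator results presented alone.

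**A joint model may still omit something.** The Abstract names food frequency as a mediator, and the Mediator Variables list also holds depression, stress and environmental supports. The set of mediators in the joint model therefore has to be stated.

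**Conclusion.** The point holds in conditional form. The mediation section commits to models with arm and one mediator, each giving a test and a proportion explained. Such models cannot separate mediators that remain correlated after adjustment for arm. Section 1 and D.2.4.2 show that the programme is meant to move several of the constructs, so one of the two necessary conditions is the plan's own intention. The other, residual correlation, is plausible but is an assumption here.

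Over r = 0.2 to 0.5, an inert mediator's chance of testing significant runs from about 2% (moved 0.1 SD, r = 0.2) to about 87% (moved 0.3 SD, r = 0.5). Reliability in the range that the protocol reports would pull the upper figures down.

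This is a worthwhile improvement to a secondary aim and not a plain error. It has no bearing on the primary MVPA comparison.

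**What to change.** Add to Mediation Analyses (Aim 2c) one parallel multiple-mediator model: MVPA change on arm and on all mediators named for Aim 2c, with baseline values, together with each mediator on arm. Settle whether food frequency belongs to the set, since section 1 omits it and the Abstract includes it. Report each specific indirect effect and the total indirect effect with intervals.

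Keep the planned single-mediator results alongside as descriptive. State that their proportions explained can overlap and must not be read as additive shares.

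The cost is a few lines of text and one more outcome regression on data already being collected. Intervals for the specific effects will be somewhat wider because the mediators are correlated. The joint model also understates a mediator that acts through another one, so both sets should be shown and neither reported alone.

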Physical Activity. We will use two measures of PA. **Accelerometers:** Participants will be instructed to wear accelerometers over seven consecutive days. The Actigraph GT3X 16Mb activity monitor is small, light weight, and designed to detect vertical acceleration that allows for the detection of normal human motion and reject high frequency vibrations encountered in activities such as operation of a lawn mower. The filtered acceleration signal is digitized and the magnitude is summed over a user-specified time interval. At the end of each interval, the summed value or activity "count" is stored in memory and the integrator is reset. For the proposed study, participant will wear the monitor for one week and a 1-minute time interval will be used. Freedson et al.^{82, 83} assessed the validity and inter-instrument reliability of the ActiGraph monitor in adults. Activity counts were strongly correlated with energy expenditure during treadmill walking and running ($r = 0.86$) We will determine the total time per day spent in moderate and vigorous PA by using adapted cut points previously established by Freedson et al.^{82, 83} Participants will need to wear the accelerometer for at least 10 hours per day and on at least 3 of the 7 days for reliable measurement of activity. [name] and [name] have used activity monitors in previous studies and had high compliance (81%) with the activity monitor protocol in the pilot study⁸⁴. (See Appendix D for accelerometer log). **Self Report:** We will use a comprehensive self-report measure to characterize participants' type, pattern, nature, and amount of PA in a typical week. The Community Health Activities Model Program for Seniors Physical Activity Questionnaire (CHAMPS) is a 41-item self-report measure of PA was developed originally for older adults, but it has been used with general adult populations^{64, 85}. We will use the measure as originally developed, but we will modify those items that are geared for older adults to be age-neutral (e.g., replace "visit a senior center" with "visit a community center"). For the proposed study, we will use total minutes per week spent in moderate and vigorous PA as the primary outcome measure. The CHAMPS has strong psychometric properties and has also been shown to be sensitive to change in intervention studies⁸⁵.

Secondary Outcome Measures:

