Qualitative Data Analysis Plan. Audio recordings of interviews will be transcribed verbatim in the source language and returned to the PI in paper and electronic (Microsoft Word) formats. A data collection assistant will review the paper transcripts for quality control purposes to make sure that the paper and electronic transcripts are as accurate and reflective of the interview as possible. All identifying information will be removed from transcripts. The transcript files will be imported into AtlasTi software for qualitative data management and analysis. All data in paper format will be stored in locked cabinets in locked offices. [name] will lead the qualitative analysis of the interview data in the source language, using thematic analysis procedures and the constant comparison method^{97,106}. For presentation and dissemination, selected excerpts of the Spanish-language qualitative data will be translated into English.

Power and Sample Size: Power calculations were conducted to determine the minimum detectable effect size based on a desired power achievement =0.80 using Optimal Design¹⁰¹. Setting the standard effect size to 0.50 and an expected intraclass correlation of .01, we have calculated a minimum number of 83 subjects per site will be needed. Based on a 76% retention rate from the pilot study, we will sample an additional 25 subjects to maintain statistical power throughout study duration for a total of 108 per site and an overall total of 864 subjects.

In-Depth Interviews: With a resulting sample of 96 interviews, we anticipate meeting the requisites of saturation and sufficiency⁹⁶. Saturation refers to the point in the study at which analysis of the interview data results in no new properties or dimensions⁹⁷. The greater the amount of pertinent (on-topic) data obtained from participants, the smaller number of participants required for saturation; thus, well-devised and conducted interviews with skilled probing reduces the need for large sample sizes in order to fully assess the phenomena under study⁹⁸. Sufficiency is the extent to which the participant sample encompasses the range of variability in the participant characteristics, especially those of known relevance to the topic⁹⁹. Due to the relative homogeneity of our participants, a sample of 96 interviews is expected to be sufficient.

6.b. List of the study intervention(s) being tested or evaluated under this protocol

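### The attrition check compares women lost to follow-up with a cohort that includes them, and does not cover women who attend without valid accelerometer data

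*Protocol*

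**What the plan says.** The Attrition Analyses paragraph in Section 6.a of the Protocol sets out four things.

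- The main comparison: "We will compare all baseline demographic, cognitive, and behavioral variables of participants lost to follow-up with baseline data of the cohort".
- The question that defines selective attrition, which the protocol treats as a threat to generalization: "do dropouts differ from the cohort as a whole".
- An example of the analyses intended: "analyses will be conducted to determine if participants with greater weight or lower PA disproportionately drop out of the study".
- A separate rule for loss by arm: "Presence of differential attrition (i.e., difference in dropouts between treatment conditions) will be considered a threat to internal validity".

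It names no test and does not define loss to follow-up. It closes by saying that the primary and secondary analyses follow intention to treat.

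Two other parts of the Protocol bear on this. The Physical Activity paragraph under Primary Outcome Measures sets a validity rule for the monitor, "Participants will need to wear the accelerometer for at least 10 hours per day and on at least 3 of the 7 days", and reports 81% compliance in the pilot. Power and Sample Size sets the recruitment margin: "Based on a 76% retention rate from the pilot study". The Abstract names accelerometer MVPA as the primary outcome, and the analysis plan for Aim 1 lists accelerometer and CHAMPS MVPA together.

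**The concern.** There are two separate problems.

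**Comparator.** The cohort as a whole includes the women who were lost. Comparing a subgroup with a total that contains it shrinks the difference, and the two groups are not independent. The usual two-sample standard error is then wrong.

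**Trigger.** The check follows women lost to follow-up. For the accelerometer outcome, loss is not the only way to be missing. A woman can attend the 16-week visit, fall short of the wear rule, and have no valid accelerometer value. On the ordinary meaning of the words she has not been lost, so nothing in the paragraph looks at her.

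At stake is the reliability of the paragraph that decides whether a validity threat from missing data is declared. A diluted table, or one that omits women who did not wear the monitor enough, could look more reassuring than it should.

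**Working it through.** **Inputs.** 864 women, 108 per site, 83 needed per site and 76% retention (Power and Sample Size); 81% pilot compliance and the wear rule (Primary Outcome Measures). Two-sided 5% for the attrition test is an assumption, since the protocol states no level for it. Clustering by CRC is ignored.

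**The plan's own use of the retention rate.** 83 / 0.76 = 109.2, or 110 after rounding up, against 108 stated; 108 × 0.76 = 82.1. The stated figure reproduces to within 3%. Overall, 864 × 0.76 = 657 retained, leaving 207 lost.

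**Dilution.** With retained fraction r:

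- cohort mean = r × completer mean + (1 − r) × dropout mean
- dropout mean − cohort mean = r × (dropout mean − completer mean)

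At r = 0.76, a true difference of 0.20 SD is shown as 0.152 SD. This is an identity and holds whatever test is used, including in a purely descriptive table.

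**If an ordinary two-sample test ignores the overlap.**

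- Dropouts v completers: SE = √(1/207 + 1/657) = 0.0797; z = 0.20 / 0.0797 = 2.51; power = Φ(2.51 − 1.96) ≈ 71%.
- Dropouts v whole cohort, treated as independent: SE = √(1/207 + 1/864) = 0.0774; z = 0.152 / 0.0774 = 1.96; power ≈ 50%.
- True SE of the diluted difference: 0.76 × 0.0797 = 0.0606. The nominal 1.96 cut-off is therefore really 1.96 × 0.0774 / 0.0606 = 2.50, a two-sided size of about 1.2%.

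**If the test allows for the overlap.** z = 0.152 / 0.0606 = 2.51, the same as dropouts v completers. Power and size are unchanged.

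**Missing accelerometer outcomes.** With compliance c among retained women (an assumption about what the 81% means):

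- missing = 1 − rc = 1 − 0.76 × 0.81 = 38.4%, about 332 women
- retained without valid wear = r(1 − c) = 0.76 × 0.19 = 14.4%, about 125 women
- share outside the check = 0.1444 / 0.3844 = 37.6%

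| Retention | Compliance | Share of missing accelerometer outcomes outside the check |
|---|---|---|
| 76% | 81% | 37.6% |
| 76% | 85% | 32.2% |
| 76% | 90% | 24.1% |
| 70% | 81% | 30.7% |
| 80% | 81% | 43.2% |

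At 76% retention the share equals one third when c = (3 × 0.76 − 1) / (2 × 0.76) = 84.2%, and is lower above that.

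**The case against.** The strongest reply is that the paragraph only says the groups will be compared. It fixes no test, standard error or threshold, so the lost power and distorted size belong to an analysis the protocol does not prescribe. That stands. A reader might infer that the plan must under-detect selective loss, but the documents do not support this: a test that respects the overlap loses no power.

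The same paragraph also asks whether heavier or less active women leave disproportionately. That is naturally read as leavers against stayers. The internal-validity rule compares dropouts between arms, which are disjoint. Neither has the overlap, and this stands too. It would be wrong to call the whole attrition plan biased toward finding nothing. What remains is that the definition of selective attrition uses the overlapping comparator, so the paragraph holds two readings of one check.

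On non-wear, handling of invalid monitor weeks is often left to the SAP, and loss to follow-up is undefined. Women without valid wear may still supply CHAMPS MVPA, so they can be missing one of two measures rather than all outcome data. This limits the point to the accelerometer measure but does not remove it: the protocol states its own trigger, and that trigger does not match its own validity rule.

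A reader might also take it as established that over a third of missing accelerometer outcomes escape the check. The documents do not establish that. The 81% has no stated denominator or time point, and Section 9.b offers a payment for sufficient data and a third visit if needed, which may raise compliance.

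Finally, the intention-to-treat analysis does not depend on this check. That is correct and bears on the weight of the point.

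**Conclusion.** The point holds in a limited form. The comparator contains the dropouts, so each baseline difference is shown at the retained fraction of its dropout-versus-completer size, 0.76 at the pilot rate. That much is certain.

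The figures of about 1.2% size and 50% against 71% power at 0.20 SD apply only if an ordinary two-sample test ignores the overlap, at two-sided 5% and without clustering.

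The check also leaves out women who attend but do not meet the wear rule. They are about 38% of missing accelerometer outcomes if the 81% applies to retained women. The share is about 24% at 90% compliance, and 31% to 43% for retention of 70% to 80% at 81% compliance. The gap exists whenever any retained woman fails the rule; only its size rests on the assumption.

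This affects a supporting check on validity, not the estimate of the intervention effect.

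**What to change.** Reword the Attrition Analyses paragraph as follows.

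- Compare the baseline variables of women without a valid outcome with those of women who have one, not with the whole cohort.
- Do this separately for accelerometer and CHAMPS MVPA, and separately at 16 and 40 weeks.
- Assess differential missingness by an arm-by-missing comparison on the baseline variables that allows for CRC.
- Tabulate the reason for missingness (lost, withdrew, non-wear) by arm.

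The cost is wording and slightly more analysis, using data already collected: baseline measures, monitor files and the retention tracking database. The downside is that more attrition signals may have to be reported. The primary estimate does not change.
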